### Aim 2.

Generalized linear mixed models (GLMMs) will be used to examine intervention effects over the course of the study. Link functions will be included as described above for the GLM models. Adherence concerns may differ in the two cohorts, thus separate models will be employed for each cohort (de novo, established). Treatment group will be the independent variable of primary interest, modeled as a fixed effect with the usual care group specified as reference group. We will also include fixed effects for site (NU, Mayo), time since transplant (in months), and potential confounding covariates noted in bivariate analyses. Random participant effects for each participant will be included to account for repeated measurements nested within each participant (assuming a compound symmetry, although we will fit autoregressive structures as well, comparing fit using AIC and BIC criterion). Outcomes recorded at each interview will be analyzed by visit whereas adherence measured by tacrolimus levels, along with blood pressure control will be analyzed in 6-month intervals as described above. A time-since-transplant-by-arm interaction term will be included to examine if outcome trajectories/slopes over time differ by study arm. Since prescription knowledge and adherence will be assessed for each medication, 2-level GLMM will be used for these outcomes with medications nested in participants. For  $\Delta$  eGFR and re-hospitalization outcomes, GLM models will be used since outcomes over 2 years are summarized in a single measurement. In the de novo cohort, change in eGFR from transplant to 2 years post-transplant and # hospitalizations (any hospitalization, if rare) within 2 years post-transplant will be modeled. For the established cohort, the time period for the both measures will span from transplant to 2-year study visit. It is possible those who do not complete the 2-year visit will differ in important characteristics (e.g. cognition, comorbidity), which could bias results. We will use collected data at prior interviews to understand the extent that individuals who complete follow-up differ from those who do not. If differences are found, pattern-mixture models will be employed by classifying participants' drop-out type or pattern (e.g. completed, refused, lost to follow up, death). This variable will then be added to mixed effects models to account for differences.

*Power Calculation.* The sample size calculation was based on the availability of 700 transplant patients estimated by the number of transplants conducted in 2012-2014 across the two sites. With the sample size set at 610 accounting for 85-90% retention at 1 year, we present the minimum differences we will be able to detect between the intervention and usual care arms for each outcome of interest. For the main outcome of medication adherence, we estimate 45% of the sample to be non-adherent using the composite score described above taking estimates for each individual measure into account. We will have sufficient power ( $\geq 80\%$ ) to detect differences of 11% in the entire sample assuming a 5% Type I error rate. Should TAKE IT be associated with potential confounders, calculations show that an R-squared of 0.2 between predictors (a conservatively high estimate under randomization), we would still maintain 70% power to detect the 11% difference. Although adjusting for confounders would decrease variability in adherence, and increase power. Detectable differences for individual adherence measures along with estimates and effect sizes for other outcomes of interest are listed in Table 5.

Table 5. Detectable Differences in Health Outcomes between Study Arms at 1 Year

Outcome	Total (n=610) 305/arm		De Novo (n=270) 135/arm		Established (n=340) 170/arm	
	Usual Care Estimate	Minimum Difference	Usual Care Estimate	Minimum Difference	Usual Care Estimate	Minimum Difference
Primary Outcomes						
Rx Knowledge, %	50	11.3	60	15.9	45	15.1
Rx Non-adherence, %	45	11.0	35	15.2	50	15.0
Self-report, %	35	10.3	29	14.1	44	14.6
Objective (pill count), %	45	11.1	35	11.3	50	15.0
Claims (PDC), %	30	9.8	23	12.7	38	14.0
Biologic (SD Tacrolimus), %	40	10.8	30	14.3	45	14.7
Secondary Outcomes						
Quality of life, mean(SD)	46.2 (9.0)	2.0	45.8 (7.2)	2.5	49.5 (9.0)	2.7
Clinical outcomes						
$\Delta$ eGFR, mean(SD)*	-5.8 (9.0)	2.9	-3.0 (11.0)	3.8	-8.0 (15.0)	4.6
Re-hospitalizations, %	40	10.8	32	14.6	47	14.8
Systolic BP, mean(SD)**	136.7 (8.3)	2.2	138.3 (12.9)	5.1	135.0 (7.9)	2.8

\* $\Delta$  eGFR estimates over 2 years

[figure not shown]
\*\*estimate 75% of cohort has hypertension (Total: n=458, 229/arm; De Novo: n=202, 101/arm; Established: n=256, 128/arm)

*Exploratory Analyses.* A single measurement for each exploratory transplant related clinical outcome (i.e. acute rejection, toxicity, infection) will be modeled at the end of the study indicating the total number of occurrences (or any for rare outcomes) over the course of the study using GLM models as described above. We recognize we likely will not have sufficient power to find differences in these outcomes. Intervention effects on blood pressure and glycemic control will be examined among those with diabetes and/or hypertension.

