## 1.0 Objectives:

### 1.1 Specific Aims and hypotheses are to:

**Aim 1:** Test the effectiveness of the TAKE IT strategy, compared to usual care, to improve kidney transplant (KT) recipients’:

**H1:** treatment knowledge (indications, potential side effects, demonstrated proper use)

**H2:** medication use (regimen adherence via self-report, pill count, tacrolimus levels)

**H3:** transplant-specific outcomes ( $\Delta$  eGFR, quality of life, re-hospitalization)

**H4:** chronic disease outcomes (blood pressure, HbA1c)

**Aim 2:** Examine the persistence of any effects of the TAKE IT strategy on outcomes over 2 years among new and established KT recipients.

**Aim 3:** Evaluate the fidelity of each component of the TAKE IT strategy over time, and investigate any patient, provider, or transplant center barriers to implementation.

**Aim 4:** Determine the costs of delivering the TAKE IT strategy from a transplant center perspective.

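### Aim 2 models the two cohorts separately and plans no comparison between them, so significance in one cohort only could be misread as persistence in that cohort only

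*Combined protocol and SAP*

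**What the plan says.** Section 1.1 gives Aim 2 as: "Examine the persistence of any effects of the TAKE IT strategy on outcomes over 2 years among new and established KT recipients".

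Section 11.1 (Aim 2) uses generalized linear mixed models and gives a possible difference in adherence concerns as the reason for splitting: "thus separate models will be employed for each cohort (de novo, established". Within each cohort model:

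- Repeated visits are handled by a patient-level random effect: "Random participant effects for each participant will be included to account for repeated measurements nested within each participant".
- The only interaction named is with time: "A time-since-transplant-by-arm interaction term will be included to examine if outcome trajectories/slopes over time differ by study arm".
- Change in eGFR and re-hospitalization are handled differently: "GLM models will be used since outcomes over 2 years are summarized in a single measurement". Their time windows differ by cohort. De novo patients are measured from transplant to 2 years after transplant, established patients from transplant to the 2-year study visit.

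Aim 1, by contrast, analyses all patients together at 1 year. It adjusts for time since transplant and examines effect modification only if an effect is found. Cohort is not named there.

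The Power Calculation paragraph claims at least 80% power "to detect differences of 11% in the entire sample assuming a 5% Type I error rate". Table 5 adds columns for each cohort, for example "De Novo (n=270) 135/arm". No power is given for the Aim 2 longitudinal models or for any comparison between cohorts.

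**The concern.** The reason given for splitting is that the cohorts may not be alike, yet two separate models neither estimate nor test that. The time-since-transplant-by-arm term sits inside a single-cohort model, so it compares the slopes of the two arms and says nothing about one cohort against the other.

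The output is two p-values, each from roughly half the patients. If one falls below 0.05 and the other does not, the easy conclusion is that TAKE IT lasts in one group and fades in the other. The same pattern arises often when the effect is identical in both. For the repeated-measures outcomes the plan holds no combined 2-year estimate, and for no outcome a between-cohort contrast, that would guard against this. At stake is the answer to Aim 2, and any later decision to offer the strategy to one group of recipients and not the other.

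**Working it through.** **Inputs.** Table 5, composite non-adherence under usual care and patients per arm: total 45%, 305; de novo 35%, 135; established 50%, 170. The text agrees on the total: "we estimate 45% of the sample to be non-adherent using the composite score". Type I error is 5%, taken as two-sided because sidedness is not stated.

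**Formula.** Two-proportion test with difference d, n per arm and mean proportion p̄:

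- SE₀ = √(2p̄(1−p̄)/n)
- SE₁ = √([p₁(1−p₁)+p₂(1−p₂)]/n)
- power = Φ((d − 1.96·SE₀)/SE₁)

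**Step 1: reproduce Table 5.**

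- Total, 45% vs 34%, 305 per arm: SE₀ 0.0396, SE₁ 0.0393, power 79.5%
- De novo, 35% vs 19.8%, 135 per arm: 80.3%
- Established, 50% vs 35%, 170 per arm: 80.2%

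The method matches the plan's figures.

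**Step 2: the same 11-point effect in both cohorts, one time point.**

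- De novo, 35% vs 24%: (0.11 − 1.96×0.0555)/0.0551 = 0.02, power 50.9%
- Established, 50% vs 39%: (0.11 − 1.96×0.0539)/0.0536 = 0.08, power 53.2%

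The cohorts hold different patients, so the tests are independent:

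- both significant: 0.509×0.532 = 27%
- exactly one: 0.509×0.468 + 0.491×0.532 = 50%
- neither: 0.491×0.468 = 23%

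The pooled comparison has 79.5% power. An inverse-variance combination stratified by cohort has SE 0.0384 and power Φ(0.11/0.0384 − 1.96), about 82%.

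**Step 3: variations, still one measurement.**

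- A common odds ratio of 0.63 (45% to 34%) in place of a common difference: 41% and 56%, exactly one 51%.
- A 24-month comparison with assumed 70–85% retention of 350 per cohort: 47–55% and 41–48%, exactly one about 50%.
- Re-hospitalization, a single-measurement Aim 2 outcome, at its whole-sample detectable difference of 10.8 points (32% and 47% under usual care): 52% and 52%, exactly one 50%.

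**Step 4: repeated measures.** Section 9.9 has five follow-up interviews. For an effect averaged over k = 5 complete visits with within-patient correlation ρ, the variance is multiplied by (1+(k−1)ρ)/k. The documents give no ρ, so 0.3 to 0.9 is an assumption.

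| ρ | Factor | De novo power | Established power | Both | Exactly one |
|---|---|---|---|---|---|
| 0.3 | 0.44 | 85% | 87% | 74% | 24% |
| 0.5 | 0.60 | 73% | 75% | 55% | 39% |
| 0.7 | 0.76 | 62% | 65% | 41% | 46% |
| 0.9 | 0.92 | 54% | 57% | 31% | 49% |

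**Step 5: Table 5's own cohort differences.** With 15.2 and 15.0 points, power is 80% in each, both are significant in 64% of trials and exactly one in 32%.

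**Step 6: what an interaction test could show.** The SE of the difference between cohort effects is √(0.0551² + 0.0536²) = 0.0769. For 80% power the gap must be about (1.96+0.84)×0.0769 = 0.215, or 21.5 points. If the effect is 11 points in one cohort and zero in the other, power is about 29%.

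**The case against.** A reader might infer three stronger things that the documents do not support.

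- *That Aim 2 as a whole has about 50% power in each cohort.* That figure is for a uniform 11-point effect, one measurement and 1-year sizes. The interview outcomes use mixed models over repeated visits, where power for an average effect could be well above 50% (Step 4). Nor does it describe power for the slope interaction, which was not calculated. Also, 11 points is the plan's whole-sample difference. Table 5 openly shows about 15 points per cohort, so the loss of precision is disclosed.
- *That significance in exactly one cohort is the most likely result under a uniform effect.* That is so for a single measurement. For an average over five visits it is so only from a correlation of about 0.65 upwards. Below that, significance in both is more likely.
- *That no overall 2-year estimate exists.* This is too broad. Aim 1 covers change in eGFR without a cohort split, Section 8.4 defines it over 24 months, and Table 5 has a total row footnoted as 2-year. The exploratory rejection, toxicity and infection analyses also state no split.

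The design also lends separate models some support. Section 11.1 describes allocation within each cohort, and the eGFR and hospitalization windows differ, so simple pooling would mix different quantities. An interaction test would itself be weak and could invite the opposite misreading. Finally, nothing in the plan says that cohorts will be compared by their p-values, and the primary 1-year analysis pools them.

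These points narrow the size of the concern and shape the remedy. They do not supply the missing cohort-by-arm estimate, nor a combined 2-year estimate for the repeated outcomes. Aim 1's effect-modification analysis is conditional, is tied to the 1-year question and does not name cohort.

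**Conclusion.** The point holds for Aim 2 only. The plan splits the cohorts because they may not be alike but never estimates how far their effects differ. If the true effect is the same 11 points in both, the chance of a significant result in exactly one cohort is about 50% for a single measurement, and 24% to 49% for a five-visit average with an assumed correlation of 0.3 to 0.9. At the larger differences that Table 5 gives for each cohort, it is 32%. These figures rest on Table 5's rates and 1-year sizes, a two-sided 5% test and, for the repeated outcomes, complete visits and a constant effect. The primary 1-year conclusion is unaffected. The change is worth making because it uses the same data and removes an avoidable ambiguity.

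**What to change.** For the repeated-measures outcomes in Aim 2, fit one mixed model on all patients with cohort, arm, time, arm-by-cohort and arm-by-time-by-cohort terms, and let the variance components differ by cohort. From that model report, in order:

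1. the combined 2-year effect;
2. the arm-by-cohort estimate with its confidence interval;
3. the cohort-specific estimates.

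State in advance that the interaction has low power (80% only for a gap of about 21.5 points on the single-measurement calculation). It is to be read as estimation, and non-significance is not to be read as equality.

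For change in eGFR and hospitalization, either analyse a window common to both cohorts, or keep the cohort-specific estimates and add a formal between-cohort contrast.

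The cost is a change of SAP wording and slightly more modelling work. No new data are needed. The confidence interval on the interaction will be wide, and the report should say so.

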**8.0 Study Endpoints:**

**8.1** The primary study endpoint will be the completion of all analysis of the Aims. A secondary study endpoint will be when all patient interviews are completed (n=700).

Table 4. Study Measures and Outcomes		Interview Timepoint				
Variable	Instrument(s) or Measure(s)	BL	6w	6m	12m	18m
Covariates		IP			IP	
Socio-demographics, patient characteristics	Age, sex, race/ethnicity, education, income, language, country of origin, time in US, others	■				
Health status (physical, mental)	Promis – anxiety & depression, global, physical	■				
Cognitive status	BTACT	■			■	
Social support	TSS; Medication Support Survey	■			■	
Health literacy	NVS, Chew	■			■	
Patient activation	CHAI	■			■	
Regimen characteristics	MRCI, drug class, cost	■		■	■	■
System Process Outcomes						
Receipt of UMS materials	Receipt of UMS (yes/no)		■	■	■	■
Medication reconciliation	Updates to medical/pharmacy records				■	
Receipt of SMS text reminders	Receipt of SMS (yes/no), satisfaction		■	■	■	■
Completion of assessment	Completion of assessment, satisfaction		■		■	
Clinic follow-up	Did clinic follow up on concerns		■		■	
Intervention impact on clinic practice	Qualitative interview with clinic staff					
Patient Effectiveness Outcomes						
Medication adherence	ASK-12, 24hr recall	■	■	■	■	■
	Pill Count	■		■		
	Proportion of Days Covered, Tacrolimus Levels			■	■	■
Treatment knowledge	General Rx knowledge, Demonstrated use, Consolidation	■	■	■	■	■
Quality of Life	PROMIS (physical, anx, dep, global)					
Clinical outcomes	Transplant related: eGFR, re-hospitalization, IFTA, acute rejection, toxicity, infection					
	Systolic blood pressure, Hemoglobin H1AC	■		■	■	
Cost Outcomes						
Programming maintenance costs for EHR	Printer ink, paper, staff time					
Running UMS technologies						
SMS monthly costs						

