## 9.9 Research Procedures

Research activities will include a baseline interview, and follow-up interviews at 6 weeks, 6 months, 12 months, 18 months and 24 months. The baseline and either the 12 month or the 18 month interview will be conducted in-person\*, while the remaining interviews will be conducted via phone. To facilitate the geographical diversity of KT patients at the Mayo Clinic, measures used in the baseline and 12 month interview can be administered in-person or via phone. If a pill count needs to be completed over the phone, a pill count tray will be sent to the participant prior to the scheduled interview.

\*If the 12-month interview cannot be done in person due to the timing of clinic visits, it will be done over the phone and we will attempt to do the 18 month interview in person.

**Pilot Testing and Refinement of Study Procedures.** We will pilot test our strategy and study protocol, including the evaluation battery and patient materials, among 10 KT recipients per site who meet established patient eligibility criteria. Cognitive interviews (~45 min.) will be conducted to finalize and/or refine all study materials. We will 1) obtain average completion times for the interview, 2) elicit patient comprehension of the interview and intervention components. Necessary modifications will be made prior to full-scale implementation.

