**11.0 Data and Specimen Management:**

**11.1 Analysis Plan.**

All analyses will be performed in SAS v9.4 (SAS Institute, Cary, NC). [name] will perform analyses under the direct supervision of Drs. [name], [name] and [name]. Drs. [name] and [name] will also provide guidance.

Aim 1.

The proposed trial uses a 1:1 randomized design that assigns patients to TAKE IT or usual care within each cohort. We will accrue approximately 700 patients (350 de novo, 350 established) anticipating 90% retention in the de novo cohort (85% established) for follow-up at 1 year, leaving a minimum 525 patients for primary analyses. High retention will be supported through close follow-up, mailed reminders, birthday cards, and a newsletter. Given the clinical follow-up necessary for KT recipients, we are confident we will achieve this goal.

Regimen adherence at one year is the primary outcome of interest for Aim 1, with Rx knowledge and individual adherence measures also of primary interest. Secondary outcomes include quality of life (PROMIS outcomes and FKSI) and the clinical outcomes of change in eGFR, and any transplant-related re-hospitalization. Blood pressure control in those taking anti-hypertensive medications will also be examined. Relationships between

adherence and potential confounders (age, comorbidity, cognitive ability, regimen complexity, internet use, dose of intervention, etc.) will also be examined. For all outcomes, we will use generalized linear models (GLMs), adjusted for confounders and study site, specifying the logit link function for binary outcomes and identity link for continuous outcomes (quality of life, change in eGFR, SBP). Treatment group will be the independent variable of primary interest, with usual care specified as reference group. We will also include time since transplant at baseline (in months), baseline value of the outcome, and any potential confounding covariates noted in bivariate analysis. For outcomes measured per medication, a generalized estimating equation (GEE) approach will be employed to adjust standard errors for within-patient correlation. Should TAKE IT have an effect on outcomes, secondary analyses will examine if any of the potential confounders considered exhibit any effect modification.

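### The Aim 2 mixed models omit the baseline value of the outcome and do not say how the baseline interview enters, which costs precision for visit-level arm differences in outcomes measured at baseline

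*Combined protocol and SAP*

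**What the plan says.** All references are to the combined protocol and SAP.

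- **Section 11.1, Aim 1.** The 1-year models adjust for site, time since transplant, "baseline value of the outcome, and any potential confounding covariates noted in bivariate analysis".
- **Section 11.1, Aim 2.** The mixed models borrow the link functions from Aim 1 but have a separate covariate list: "We will also include fixed effects for site (NU, Mayo), time since transplant (in months), and potential confounding covariates noted in bivariate analyses". The baseline outcome is not named and no reason is given.
- **Response rows.** The plan says "Outcomes recorded at each interview will be analyzed by visit". Section 9.9 says "Research activities will include a baseline interview, and follow-up interviews at 6 weeks, 6 months, 12 months, 18 months and 24 months", so baseline is itself an interview. Whether it supplies a response row is not stated.
- **Contrast and correlation.** Treatment group is the variable of main interest. In addition, "A time-since-transplant-by-arm interaction term will be included to examine if outcome trajectories/slopes over time differ by study arm". Participant effects are random, "assuming a compound symmetry, although we will fit autoregressive structures as well", with fit compared by AIC and BIC. De novo and established cohorts are modelled separately.
- **Outcomes outside the mixed models.** For change in eGFR and re-hospitalization, "GLM models will be used since outcomes over 2 years are summarized in a single measurement".
- **Table 4 (section 8).** Baseline is marked for ASK-12 and 24-hour recall, pill count, knowledge, and SBP/HbA1c. It is not marked for "Proportion of Days Covered, Tacrolimus Levels".

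**The concern.** The text allows two readings, and neither uses baseline well for the arm effect.

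1. Baseline is neither a covariate nor a response row. Its information is then lost.
2. Baseline is a response row and the arms may differ there. In a by-visit model, the arm difference at a later visit then gains nothing. If the effect is read as change from baseline, it is noisier than an adjusted comparison.

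Precision is scarce in Aim 2 because each cohort is fitted alone: Table 5 has 135 and 170 patients per arm at 1 year, with detectable differences in non-adherence of 15.2 and 15.0 points. The power section itself notes that covariate adjustment would raise power. What is at stake is efficiency and sensitivity to chance imbalance at baseline. Randomisation prevents bias in expectation, and the Type I error rate is not in question.

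**Working it through.** **Inputs from the documents.** Follow-up at 1.5 (6 weeks), 6, 12, 18 and 24 months; compound symmetry first, autoregressive also fitted; Table 5 sample sizes and SDs. **Assumed.** Baseline-to-follow-up correlation r of 0.3, 0.5 or 0.7; a continuous outcome; complete data; two-sided 5%. Under autoregressive decay, r is the correlation at 12 months.

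**1. The plan's own figures.** No power or precision is stated for the Aim 2 mixed models. The 1-year claim does reproduce. For 45% against 34% with 305 per arm, the null SE is √(2×0.395×0.605/305) = 0.0396 and the alternative SE is √((0.45×0.55+0.34×0.66)/305) = 0.0393. Then (0.11 − 1.96×0.0396)/0.0393 = 0.82, a power of 79.5% against the stated 80% or more.

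**2. Arm difference at month 24, compound symmetry.** Variance relative to a model without baseline:

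| r | Baseline omitted | Change from baseline, 2(1−r) | Baseline used, 1−r² | Saving vs omitted | Saving vs change |
|---|---|---|---|---|---|
| 0.3 | 1 | 1.40 | 0.91 | 9% | 35% |
| 0.5 | 1 | 1.00 | 0.75 | 25% | 25% |
| 0.7 | 1 | 0.60 | 0.51 | 49% | 15% |

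The factor 1−r² is the same whether baseline is a covariate or a response row with a common mean in both arms. A response row with the arms free gives a factor of 1 for the month-24 difference, so no gain.

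**3. Month 24, autoregressive decay.** The correlation with baseline falls to r², so the factor is 1−r⁴ = 0.992, 0.938, 0.760. The saving is 1%, 6% and 24%.

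**4. Average of the five follow-up visits, compound symmetry.** Omitted: (1+4r)/5 = 0.44, 0.60, 0.76. Baseline used: subtract r², giving 0.35, 0.35, 0.27, a saving of 20%, 42% and 64%. Change from baseline: add 1−2r to the omitted value, giving 0.84, 0.60, 0.36, against which the saving is 58%, 42% and 25%.

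**5. Arm-by-time slope, compound symmetry.** With a common entry time, the slope variance is proportional to (1−r)/Σ(t−t̄)².
- Five follow-up visits: Σ(t−t̄)² = 1082.25 − 5×12.3² = 325.8. Adding a baseline covariate changes only the part of the covariance shared by all visits, so the slope variance is unchanged (0%). With the established cohort's entry times assumed spread over 6-24 months, the cut is 3-6%.
- Baseline as a sixth row: 1082.25 − 6×10.25² = 451.9. The variance ratio is 325.8/451.9 = 0.72, a 28% cut (26-27% in the established cohort). Going the other way, dropping a baseline row raises slope variance by 451.9/325.8 − 1 = 39%.
- Baseline row with the arms equal at baseline and a straight line from there: the information is 1082.25 − 61.5²×r/(1+5r) = 628.4, 541.9, 493.9. The variance is 451.9 over these, or 0.72, 0.83 and 0.91 of that with the arms free. This gain needs the line to start at baseline; if a separate post-baseline step by arm is added, the slope variance returns to the covariate result.

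**6. In outcome units.** The detectable difference is 2.80×SD×√(2/n), multiplied by √(1−r²) when baseline is used. The sample sizes are those for 1 year, as no 2-year retention is given.

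| Table 5 row | Stated | Recomputed | r = 0.3 | 0.5 | 0.7 |
|---|---|---|---|---|---|
| SBP, established (SD 7.9, 128/arm) | 2.8 | 2.77 | 2.64 | 2.40 | 1.98 |
| SBP, de novo (SD 12.9, 101/arm) | 5.1 | 5.09 | 4.85 | 4.40 | 3.63 |
| Quality of life, established (SD 9.0, 170/arm) | 2.7 | 2.73 | 2.61 | 2.37 | 1.95 |

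These illustrate a single visit. The quality-of-life row in Table 4 carries no visit marks as read, although PROMIS is marked at baseline among the covariates.

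**The case against.** The strongest reply is that Aim 2 asks about persistence, and its explicit trajectory test is the arm-by-time slope. Under compound symmetry, the starting structure, a baseline covariate does nothing for that slope. If baseline is already a response row, replacing it with a covariate loses slope precision (step 5). This stands, and it decides the form of the fix. It does not dispose of the point, because treatment group is also named as the variable of main interest and outcomes are analysed by visit.

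Three stronger inferences are tempting, and the documents do not support them.

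- *Every Aim 2 interval is wider than it need be.* PDC and tacrolimus levels have no baseline mark in Table 4, so the full five-measure adherence composite cannot be formed at baseline on that schedule either. Re-hospitalization has no baseline value. The eGFR change already contains its starting value at transplant.
- *The gain is large.* That depends on a correlation the documents do not give and on a structure left to AIC and BIC. At month 24 the saving could be as little as 1%.
- *A covariate and a common baseline mean are interchangeable.* They agree for visit-level differences but not for the linear slope.

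Two smaller replies also have force. Baseline values could still enter through the bivariate screen, so the plan is silent and does not exclude them; but a screen does not guarantee their inclusion. Many adherence outcomes are binary with a logit link, where adjustment changes the odds ratio being estimated, so the percentages above do not carry over directly.

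**Conclusion.** The point holds in limited form. Aim 2 omits a covariate that Aim 1 includes, gives no reason, and leaves the role of the baseline interview open. On either reading, arm differences at or averaged over follow-up visits are less precise than the collected data allow, for outcomes with a baseline measurement.

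Against a model that leaves baseline out, the month-24 variance saving for a continuous outcome is about 9-49% under compound symmetry and 1-24% under autoregressive decay. Both ranges rest on an assumed correlation of 0.3 to 0.7. For the slope under compound symmetry, a baseline main effect saves 0% (de novo) to 6% (established). This is a worthwhile correction to a longitudinal analysis, with no bias or error-rate problem behind it. The 1-year primary analysis already lists the baseline value and is unaffected.

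**What to change.** In section 11.1, Aim 2, add a statement to this effect: for each outcome measured at baseline, the baseline interview is a response row and the two arms share a common baseline mean. This gives the visit-level gain in a by-visit model and keeps the slope information in a linear one.

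For that constraint to work, the arm-by-time term must be zero on the baseline row, for example arm by months since the baseline interview. Months since transplant differ between patients at entry, especially in the established cohort.

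Where the contrast is an arm difference at a visit or averaged over visits, the plan may instead use the baseline value as a fixed-effect covariate with post-randomisation rows only. It should say which form applies to which contrast, because the two differ for the linear slope. It should also list the outcomes with no baseline value, to which neither form applies.

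The cost is a few lines of text and some model coding. The baseline data are already scheduled, so no visit, measurement or patient is added. The change should be fixed before outcome data are compared by arm.
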